3.3 Treatments

3.3.1 Treatments Administered

Due to the cross-over study design, all subjects will receive both NB-001 and placebo capsules. Each NB-001 capsule contains 100 mg of the active ingredient. Placebo capsules contain excipients only and match the NB-001 capsules in appearance.

NB-001 and matching placebo will be supplied to the Investigator or designee in blinded plastic bottles, each containing 40 capsules.

NB-001 or placebo capsules will be administered orally to the subject. Subjects will take two capsules BID, two in the morning and two in the evening (i.e., four capsules daily). The subject will begin dosing for Treatment Period 1 on the morning of Day 1, after collection of pre-dose samples. Similarly, the subject will begin dosing for Treatment Period 2 on the morning of Day 50 after collection of pre-dose samples.

3.3.2 Method of Assigning Subjects to Treatment Groups

Upon confirmation of trial eligibility, subjects will be randomized at the conclusion of the Screening Visit. Randomization will occur in a 1:1 ratio to one of two treatment sequences: NB-001 followed by placebo or placebo followed by NB-001.

3.3.3 Blinding Procedures

The randomization scheme will be generated using a computer program and verified for accuracy using strict quality control procedures. Each IP bottle will be labeled with a unique bottle number which will correspond to the randomization code and blinded treatment assignment.

In the event of a medical emergency in which it is important for the treating physician to know the treatment assignment, the blind may be broken by the Investigator. Whenever possible (i.e., if time allows), the Investigator will contact the Medical

Confidential Page 10 of 28

Monitor, or designee, prior to accessing the treatment code for the subject. Instructions for emergency unblinding of treatment codes by the Investigator will be provided in a separate data access plan.

3.4 Efficacy and Safety Variables

3.4.1 Efficacy Variables

3.4.1.1 Primary Efficacy Variable

The primary efficacy endpoint is the Clinical Global Impression-Improvement (CGI-I) score per the central rater.

The CGI-I scale will be performed by a central rater and where possible (i.e., optional), a local rater. The CGI-I assessments at Days 14, 28, 42 and 49 will use the Day 0 Clinical Global Impression-Severity (CGI-S) baseline rating as a reference for change. The CGI-I assessments at Days 63, 77, 91 and 119 will use the Day 49 CGI-S baseline rating as reference for change.

The CGI-S scale will be used to establish the degree of disease severity for each subject. The CGI-I scale will be used as an outcome measure for estimating level of functioning in response to treatment. The clinician's global assessments of the severity of the symptoms and changes in symptoms from baseline (Day 0 or Day 49, per above) will be based on reports from the subject and/or parent/guardian, and minimal direct observation (Guy 1976; Busner and Targum 2007).

At the visits noted in the schedule of assessments, the rater(s) will assess the subject's improvement relative to his/her symptoms at baseline (Day 0 or Day 49, per above) using a 7-point scale ranging from 1 (very much improved) to 7 (very much worse).

3.4.1.2 Secondary Efficacy Variables

Secondary efficacy endpoints include the following assessments:

CGI-S

The CGI-S scale will be used to rate the severity of the subject's condition on a 7-point scale ranging from 1 (Normal, not at all ill) to 7 (Among the most extremely ill subjects). It will be administered at Screening and Days 0 and 49 prior to dosing, and at additional visits noted in the schedule of assessments.

Pediatric Anxiety Rating Scale (PARS)

The PARS is a clinician-rated instrument for assessing, over time, the severity of anxiety symptoms that are associated with common Diagnostic and Statistical Manual of Mental Disorders, Fifth Edition (DSM-5) (American Psychiatric Association 2013), anxiety disorders (GAD, SAD, and SoP) in subjects aged 6 to 17 years. The PARS includes two sections. The first section is a 50-item symptom checklist, which the clinician rates as present or absent during the past week. The second section is comprised of 7 severity/impairment items that are rated on a 6-point Likert scale. The 7 severity/impairment items reflect the severity/impairment of all symptoms noted in

Confidential Page 11 of 28

Section 1 of the PARS (during the previous week) (Research Units on Pediatric Psychopharmacology Anxiety Study Group 2002). The clinician will interview both the subject and the parent/guardian to complete this assessment at the visits described in the schedule of assessments. The PARS severity score is calculated as the sum of items 2, 3, 5, 6, and 7 and will be provided in the external data transfer along with the individual item scores.

Attention Deficit Hyperactivity Disorder-Rating Scale-5 (ADHD-RS-5)

The ADHD-RS-5 will be administered at the visits noted in the schedule of assessments to document the subject's ADHD symptoms over the previous week. The ADHD-RS-5 Home Version is a parent/guardian reported scale that was developed to measure the behaviors of children with ADHD, with separate forms for children (ages 5-10 years) and adolescents (11-17 years). The ADHD-RS-5 consists of 18 items designed to reflect the symptomatology of ADHD based on the DSM-5 criteria. Each item will be scored on a scale ranging from 0 (reflecting no symptoms) to 3 (reflecting severe symptoms). items will be grouped into two subscales: inattention hyperactivity/impulsivity. The Inattention subscale raw score is computed by summing the item scores for Items 1 through 9 and the Hyperactivity-Impulsivity subscale raw score is computed by summing the item scores for Items 10 through 18. Both subscale scores will be recorded on the electronic case report form (eCRF).

Additionally, the ADHD-RS-5 incorporates two impairment scales keyed to the inattention and hyperactivity-impulsivity dimensions, which allow the clinician to assess the extent to which ADHD-related problems adversely affect the home and/or school functioning of children and adolescents (DuPaul et al. 2016). Further details are provided in Appendix 4 of the clinical study protocol.

Social Responsiveness Scale, Second Edition (SRSTM-2)

The SRSTM-2 identifies the presence and severity of social impairment within the autism spectrum and differentiates it from that which occurs in other disorders. It is a 65-item, parent completed questionnaire which incorporates 5 content areas of social deficits: social awareness, social cognition, social communication, social motivation, and autistic mannerisms. The SRSTM- 2 will be proctored by the local rater and derived and subscale raw and T-data scores will be reported on the eCRF (Constantino et al. 2003; Constantino and Gruber 2005). Further details are provided in Appendix 5 of the clinical study protocol.

3.4.2 Safety Variables

Safety assessments will include monitoring and recording of adverse events (AEs), clinical laboratory tests, vital sign measurements, physical exam, electrocardiograms (ECGs), and the Columbia–Suicide Severity Rating Scale (C-SSRS).

3.4.2.1 Adverse Events

An AE is defined as any untoward medical occurrence in a clinical investigation subject administered an IP and which does not necessarily have a causal relationship with the product. An AE can therefore be any unfavorable and unintended sign (including an abnormal laboratory finding), symptom, or disease temporally associated with the use

Confidential Page 12 of 28

of a pharmaceutical product, whether or not it is considered related to the pharmaceutical product.

Pre-existing events that increase in frequency or severity in nature during or as a consequence of use of an IP will also be considered as AEs. Any medical condition or clinically significant laboratory abnormality with an onset date before the date of informed consent signature is pre-existing and should be documented as medical history. Any AE that occurs between the date of informed consent signature and the date/time of first IP administration will be considered a pre-treatment-emergent AE. Any AE that occurs after the date/time of first IP administration will be considered a treatment-emergent adverse event (TEAE).

A treatment-emergent adverse event of special interest (TEAE-SI) is an AE of scientific and medical concern specific to the Sponsor's IP/device or program, which may warrant ongoing monitoring and/or rapid communication by the investigator to the Sponsor or designee. Such an event might warrant further investigation in order to characterize and understand it. TEAEs-SI in this trial will include: development of psychotic symptoms, suicidal ideation and behavior (SIB), seizure, overdose with untoward medical sequalae, and confirmed cases of COVID-19.

All AEs will be assessed for severity according to the Common Terminology Criteria for Adverse Events (CTCAE) Version 5.0 (effective 27 November 2017).

3.4.2.2 Laboratory Parameters

Clinical laboratory tests will include chemistry, hematology, and urinalysis as listed below in Table 2. Samples will be obtained at the Screening visit, Day 0, Day 42, Day 91/Early Termination (ET), and Day 119/EOT Visits.

Table 2 Clinical Laboratory Tests

Chemistry	Hematology	Urinalysis
Alkaline phosphatase	Hemoglobin	Glucose
Aspartate aminotransferase	Hematocrit	Protein
Alanine aminotransferase	Mean corpuscular hemoglobin	Specific gravity
Total bilirubin	Mean corpuscular hemoglobin	pН
Total protein	concentration	Nitrite
Albumin	Mean corpuscular volume	Bilirubin
Glucose	Erythrocyte count	Urobilinogen
Carbon dioxide	Leukocyte count	Ketone
Blood urea nitrogen	Neutrophil count and percentage	Blood
Creatinine	Lymphocyte count and	Leukocyte esterase
Sodium	percentage	
Potassium	Monocyte count and percentage	Other
Chloride	Eosinophil count and percentage	eGFR (Screening
Calcium	Basophil count and percentage	only, revised
	Platelet count	Schwartz
		equation)

Confidential Page 13 of 28

Other laboratory tests will include serum and urine pregnancy tests in females of childbearing potential, and urine drug tests.

Reports containing these laboratory test results will be generated by the laboratory performing the tests. Laboratory values outside of the normal range will be assessed for clinical significance by the Investigator. Abnormal laboratory tests may be repeated at the discretion of the Investigator or Sponsor.

3.4.2.3 Vital Signs

Vital signs will include blood pressure (systolic and diastolic), heart rate, respiratory rate, and temperature and will be performed after the subject has been at rest in the seated position for at least 5 minutes. Vital signs will be assessed at the Screening Visit and as clinically indicated per the schedule of assessments.

3.4.2.4 Physical Examination

A complete physical examination will be performed at the Screening Visit, Day 0, Day 42, Day 91/ET Visit, and Day 119/EOT Visit, and will include an assessment of the following body systems: general appearance; weight; height (at the Screening Visit only) mental status; head, eyes, ears, nose, and throat; dermatologic; cardiovascular; respiratory; gastrointestinal; musculoskeletal; and neurological at Screening. Additional body systems may be examined at the Investigator's discretion. An abbreviated, clinically focused physical examination based on the Investigator's clinical judgement will be administered at all other assessment intervals or as clinically indicated.

3.4.2.5 Electrocardiogram

A 12-lead ECG in triplicate will be obtained at the at the Screening Visit, Day 0, Day 42, Day 91/ET Visit, and Day 119/EOT Visit, with the subject in a supine position following at least a 5-minute rest. The Investigator will review and report the results of each ECG; the reviews on Days 42 and 91 will include a comparison of each ECG to the Day 0 ECG.

3.4.2.6 Columbia-Suicide Severity Rating Scale

Consistent with Food and Drug Administration (FDA) Guidance, *Guidance for Industry Suicidal Ideation and Behavior: Prospective Assessment of Occurrence in Clinical Trials*, (FDA 2012), the C-SSRS is used to evaluate SIB. The scale consists of 10 categories with binary responses (yes/no) to assess the subject's suicidal thoughts. An additional question regarding self-injurious behavior without suicidal intent will be evaluated with a binary response (yes/no). The C-SSRS will be used at the visits noted in the schedule of assessments to evaluate the subject's suicidal tendencies.

3.5 Data Quality Assurance

Report summaries will be generated using validated Base SAS® software, version 9.4 or higher, on a PC or server-based platform. Additional validated software may be used to generate analyses, as needed.

Confidential Page 14 of 28

All SAS programs that create outputs or supporting analysis datasets will be validated by a second statistical programmer or biostatistician. At a minimum, validation of programs will consist of a review of the program log, review of output or dataset format and structure, and independent confirmatory programming to verify output results or dataset content. Additionally, all outputs will undergo a review by a senior level team member before finalization.

The content of the source data will be reviewed on an ongoing basis by project statistical programmers and statisticians. Data will be checked for missing values, invalid records, and extreme outliers through defensive programming applications, analysis-based edit checks, and other programmatic testing procedures. All findings will be forwarded to the project data manager for appropriate action and resolution.

4. STATISTICAL METHODS

4.1 General Methodology

Data will be analyzed by Emanate biostatistics personnel. Statistical analyses will be reported with tables, figures, and listings, presented in rich text format, and using recommended ICH numbering. Output specifications for all tables, figures, and listings will be in conformance with guidelines specified by the ICH in Appendix 7 of the Electronic Common Technical Document Specification (Apr 2003).

4.1.1 Reporting Conventions

Tables and figures will be summarized by either treatment sequence or treatment group, as further described in Section 4.4 and Section 4.5 of the SAP. In general, all data collected and any derived data will be presented in subject data listings, for all enrolled subjects. Listings will be ordered by site, subject number, treatment sequence, treatment group, and assessment or event date. The treatment sequence presented in listings will be based on the planned assignment, unless otherwise noted.

In general, continuous variables will be summarized to indicate the study population sample size (N), number of subjects with available data (n), mean, standard deviation (SD), median, first (Q1) and third (Q3) quartiles, minimum, and maximum values. Categorical variables will be summarized by the population size (N), number of subjects with available data (n), number of subjects in each category, and the percentage of subjects in each category. Unless otherwise noted, the denominator to determine the percentage of subjects in each category will be based on the number of subjects with available data. Select ordinal data may be summarized using both descriptive statistics and counts and percentages of subjects in each category, as appropriate.

Non-zero percentages will be rounded to one decimal place. Rounding conventions for presentation of summary statistics will be based on the precision of the variable of summarization, as it is collected in its rawest form (i.e., on the eCRF or as provided within an external file) and are outlined as follows:

 The mean and median will be rounded to one more decimal place than the precision of the variable of summarization;

Confidential Page 15 of 28

- Measures of variability (e.g., SD, standard error [SE]) will be rounded to two more decimal places than the precision of the variable of summarization; and
- Minimum and maximum values will be presented using the same precision as the variable of summarization.

Other statistics (e.g., confidence intervals [CIs]) will be presented using the same general rules outlined above, or assessed for the most appropriate presentation based on the underlying data.

Unless otherwise specified, statistical significance testing will be two-sided and performed using α =0.05. P-values will be reported for all statistical tests, rounded to four decimal places. P-values less than 0.0001 will be displayed as "<0.0001." P-values greater than 0.9999 will be displayed as ">0.9999." Tests of interaction terms, if applicable, will be two-sided and performed using α =0.10.

4.1.2 Summarization by Visit

Data summarized by study visit will be based on the nominal, scheduled visit label as reported on the eCRF for each treatment group. Each treatment period consists of 42 days and study visits in Treatment Period 2 will be labeled according to the respective day within that treatment period. For example, the Day 63 visit occurs during Treatment Period 2 and will be labeled as Day 14 within that period. Data collected for the last subject treatment visit completed within each treatment period will be summarized separately for:

- The scheduled visit for those subjects who complete the scheduled end of treatment visit in each treatment period per protocol. This will be the scheduled Day 42 for subjects in Treatment Period 1 and Day 91 for subjects in Treatment Period 2. This summary will be labeled as "Day 42" in the analysis; and
- The last treatment visit completed on-study, combining data collected for subjects who complete the scheduled end of treatment visit, as well as the visit data for those subjects who discontinue the study early. This summary will be labeled as "Day 42/ET" in the analysis.

Data collected at unscheduled visits within the double-blind treatment period will not be included in by-visit summaries, but will be considered when endpoint derivations potentially include multiple visits (e.g., determination of baseline value, determination of worst post-baseline value, etc.). All data will be included in subject listings.

Any summarization of data collected during the follow-up period will be presented separately and will be based on the nominal, scheduled visit label as reported on the eCRF.

4.1.3 Data Handling Rules

Unless otherwise noted, values reported as greater than or less than some quantifiable limit (e.g., "< 1.0") will be summarized with the sign suppressed in summary tables and figures, using the numeric value reported. Data will display on subject listings to include the sign.

Confidential Page 16 of 28

4.1.4 Standard Calculations

Where appropriate, the calculated study day of each assessment or event will be presented with the assessment or event date on subject data listings, where study day will be determined as:

- The assessment/event date minus the date of first dose of IP, if the assessment/event date is prior to the date of first dose; and
- The assessment/event date minus the date of first dose of IP, plus one, if the assessment/event date is on or after the date of first dose.

Unless otherwise noted, study day will be calculated relative to the date of first dose of IP

Other variables requiring calculations will be derived using the following formulas:

- **Days:** A duration between two dates expressed in days will be calculated using the following conventions:
 - Later date earlier date + 1, if the earlier date is on or after the date of first dose of IP; or
 - Later date earlier date, if the earlier date is prior to the date of first dose of IP.
- **Months:** A duration expressed in months will be calculated by dividing the duration in days by (365.25 / 12).
- Years: A duration expressed in years will be calculated by dividing the duration in days by 365.25.
- **Change from Baseline:** Change from baseline will be calculated as the post baseline value minus the baseline value.
- **Percentage Change from Baseline:** Percentage change from baseline will be calculated as the change from baseline divided by the baseline value, multiplied by 100.

4.2 Analysis Sets

The analysis sets are defined as follows:

- Enrolled Analysis Set (ENR): The ENR consists of all subjects who meet all
 eligibility criteria and consent to participate in the study. All listings will be
 based on the ENR unless otherwise noted.
- Full Analysis Set (FAS): The FAS consists of ENR subjects who have at least one valid post-baseline efficacy evaluation within each treatment period. Subjects will be analyzed based on the treatment to which they were randomized. Subjects in the FAS are referred to as evaluable subjects.

Confidential Page 17 of 28

- Safety Analysis Set (SAF): The SAF consists of all subjects who receive at least one capsule (100 mg) of IP. Subjects will be analyzed based on the treatment received.
- Per Protocol Analysis Set (PPS): The PPS includes all subjects in the FAS who
 have no major protocol violations. Subjects will be analyzed based on the
 treatment received.

Data summaries to be presented on the SAF, FAS, and PPS will only be produced on all three analysis sets if there is a difference in the population groups.

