All subjects will receive NB-001 for 6 weeks, during Treatment Period 1 or Treatment Period 2, based upon their randomized treatment sequence: NB-001 followed by placebo (treatment sequence A/P) or placebo followed by NB-001 (treatment sequence P/A).

Duration of Treatment:

Each subject will participate in the trial for up to approximately 21 weeks, including a Screening period of up to approximately 4 weeks, two 6-week treatment periods with an intervening 1-week wash-out, followed by an End of Trial Visit 4 weeks after the final dose.

Reference Therapy, Dosage and Mode of Administration:

Matching placebo capsules will be administered orally BID with liquids or, if the subject is unable to swallow a capsule whole, capsules may be opened, and the contents sprinkled on applesauce.

All subjects will receive placebo for 6 weeks, during Treatment Period 1 or Treatment Period 2, based upon their randomized treatment sequence: NB-001 followed by placebo (treatment sequence A/P) or placebo followed by NB-001 (treatment sequence P/A).

Statistical Methods:

Full details of the statistical analyses will be provided in the Statistical Analysis Plan, which will be finalized before the database lock.

Summaries of baseline patient characteristics will be presented by treatment sequence and for all subjects combined. Efficacy and safety endpoints will be summarized by treatment groups.

Efficacy analyses will be conducted using the intent-to-treat principle on the full analysis set, which will include all subjects who receive at least 1 complete daily dose of IP (400 mg) and have at least 1 post-baseline efficacy evaluation within each treatment period. Safety analyses will be conducted on the safety population, which will include all subjects who receive at least 1 capsule (100 mg) of IP.

Continuous variables, including ordinal variables, will be summarized with descriptive statistics (number evaluated, mean, standard deviation, median, minimum, and maximum). Categorical variables will be presented as counts and percentages within each category. As appropriate, 95% confidence intervals will be included. All statistical testing will be conducted at a 2-sided significance level of 0.05 and considered exploratory in nature.

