7.3.2. Notification of Subject Withdrawal and Subject Termination Procedures

The Investigator must notify the Sponsor as soon as possible if any subject prematurely discontinues from the trial. The date when the subject is withdrawn from the trial and the primary reason(s) for discontinuation must be recorded in the case report form (CRF). A subject will be considered "lost to follow-up" only after reasonable, documented attempts to reach the parent/guardian prove unsuccessful. In all cases, a reasonable effort must be made to determine the reason(s) that a subject fails to return for required trial visits or discontinues from the trial.

If a subject is withdrawn from the trial early (regardless of the cause), all of the Day 91/Early Termination (ET) Visit evaluations are to be performed at the time of withdrawal (i.e., as soon as possible after the last dose of IP), to the extent possible. After completion of the Day 91/ET Visit, subjects will be followed for an additional 4-week period. All procedures and assessments noted in Table 3 for the End of Trial Visit will be performed 4 weeks after the last dose of IP to assess safety.

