7.3.3. Subject Replacement

At the discretion of the Sponsor, subjects who discontinue from the trial early may be replaced.

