15.1. Analysis Sets

The following analysis sets will be used in the trial:

- Enrolled Analysis Set (ENR): The ENR consists of all subjects who meet all eligibility criteria and receive at least 1 complete daily dose (400 mg) of IP.
- Full Analysis Set (FAS): The FAS consists of ENR subjects who have at least 1 valid post-baseline efficacy evaluation within each treatment period. Subjects will be analyzed based on the treatment to which they were randomized. Subsets in the FAS are referred to as evaluable subjects.
- Safety Analysis Set (SAS): The SAS consists of all subjects who receive at least 1 capsule (100 mg) of IP. Subjects will be analyzed based on treatment received.
- Per Protocol Analysis Set (PPS): The PPS consists of FAS subjects who do not have major protocol deviations. Subjects will be analyzed based on the treatment received.

Efficacy analyses will be conducted using the FAS, with sensitivity analyses performed using the PPS.

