4.4 Efficacy Evaluation

4.4.1 Datasets Analyzed

All efficacy summaries will be based on the FAS; select efficacy summaries will also be produced on the PPS as a sensitivity analysis. A data listing of subjects excluded from the FAS or PPS, to include the reason for exclusion, will be presented.

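### The Full Analysis Set requires an efficacy rating in both periods, so anyone who leaves in Period 1 or the wash-out is lost to every efficacy analysis

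*SAP*

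**What the plan says.** Protocol 15.1 and SAP 4.2 agree on the rule. The protocol reads "The FAS consists of ENR subjects who have at least 1 valid post-baseline efficacy evaluation within each treatment period". The SAP repeats it, "The FAS consists of ENR subjects who have at least one valid post-baseline efficacy evaluation within each treatment period", and adds "Subjects in the FAS are referred to as evaluable subjects". SAP 4.4.1 states "All efficacy summaries will be based on the FAS"; the per-protocol set, used for sensitivity, is a subset of the FAS. The primary estimand in SAP 4.4.4 is defined for the FAS. SAP 4.7 records a change to the enrolled set but leaves the both-periods condition as it was.

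Other parts of the plan point the other way:

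- Protocol synopsis, Statistical Methods: "Efficacy analyses will be conducted using the intent-to-treat principle on the full analysis set", in the same sentence as the both-periods condition.
- Protocol 7.3.2, for early withdrawals: "all of the Day 91/Early Termination (ET) Visit evaluations are to be performed at the time of withdrawal". Efficacy ratings are thus collected from subjects who leave in Period 1.
- SAP 4.1.2 plans a Day 42/ET summary that combines end-of-treatment data for completers "as well as the visit data for those subjects who discontinue the study early".
- SAP 4.5 keeps all available data from subjects who do not complete both periods, but for safety only.
- Protocol 7.3.3: at the sponsor's discretion, "subjects who discontinue from the trial early may be replaced".

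**The concern.** Membership of the FAS depends on what happens after randomization: remaining through Period 1 and the wash-out, then being rated in Period 2. If leaving is related to response or tolerability, and the rate or pattern differs by treatment, the retained subjects are a selected group. Protocol 7.3.1 lists symptomatic deterioration and adverse events among the withdrawal reasons, so outcome-related dropout is foreseeable. Dropout of poor responders mainly on NB-001 would flatter NB-001; mainly on placebo, the reverse.

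The Period 1 comparison is the most exposed. It is a comparison between separate subjects, the only one free of carryover, and it needs no Period 2 rating. The per-protocol sensitivity analysis cannot reveal the problem because it inherits the exclusion.

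**Working it through.** **1. Who is excluded**

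| Subject | In FAS? |
|---|---|
| Leaves in Period 1 after at least one rating | No |
| Leaves in the wash-out with Day 14, 28 and 42 ratings | No (Day 49 is the Period 2 baseline) |
| Leaves in Period 2 with no valid Period 2 rating | No |
| Leaves in Period 2 after a valid Period 2 rating | Yes |

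The efficacy version of Day 42/ET can therefore add early leavers from Period 2 only.

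**2. Whether the models need the rule**

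The pooled model (SAP 4.4.4) has a random subject effect and uses observed data without imputation (SAP 4.4.7.2), so it accepts subjects with one period. The by-period model (SAP 4.4.5) has treatment, visit, their interaction and baseline; it compares separate subjects. Only the paired tests need both periods: the Wilcoxon signed-rank test (Protocol 15.4) and McNemar's test (SAP 4.7).

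**3. How many subjects**

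Inputs from the synopsis: 30 evaluable, 10% dropout. 30 / (1 − 0.10) = 33.3, rounded up to 34, which reproduces the plan's figure. So 34 − 30 = 4 subjects (10% of 34 is 3.4) are expected to be non-evaluable. If all were in one sequence of 17, that is 3/17 = 18% to 4/17 = 24%.

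**4. Simple size of effect in Period 1**

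Dropping m leavers from an arm of 17 moves its mean by (m/17) × gap, where gap is how much worse the leavers score than those retained. With an assumed gap of 1 to 3 CGI-I points:

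- m = 2: 0.12 to 0.35
- m = 4: 0.24 to 0.71

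**5. Simulation**

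From the plan: 34 subjects, 1:1, SD 1.25. Assumed: the between-period and within-period correlations shown in the table; leavers go after Day 28, drawn with weight exp(2 × standardized Day 28 rating). Each scenario had 1500 trials, fitted by REML with a random subject effect, an unstructured within-period covariance and the planned fixed effects, with the Day 42 contrast. Low CGI-I is good, so negative bias favours NB-001. Monte Carlo SE is 0.006 to 0.008 pooled and about 0.012 in Period 1.

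| Leavers (between/within correlation) | Pooled bias: FAS; all observed | Period 1 bias: FAS; all observed |
|---|---|---|
| 4 on NB-001 (0.2/0.65) | −0.084; 0.006 | −0.253; 0.000 |
| 4 on NB-001 (0.4/0.65) | −0.047; 0.008 | −0.250; 0.002 |
| 3 on NB-001 (0.2/0.65) | −0.062; 0.007 | −0.193; 0.000 |
| 3 on NB-001 (0.5/0.65) | −0.018; 0.009 | −0.191; 0.002 |
| 4 on NB-001 (0.1/0.8) | −0.132; −0.005 | −0.313; −0.002 |
| 4 worst on NB-001 (0.1/0.8) | −0.160; −0.005 | −0.379; 0.000 |
| 3 NB-001, 1 placebo (0.2/0.65) | −0.037; 0.007 | −0.125; −0.001 |
| Equal split of 4 (0.2/0.65) | 0.005; 0.006 | −0.007; −0.004 |
| 4 on NB-001, driven by unseen Day 42 (0.2/0.65) | −0.143; −0.071 | −0.388; −0.203 |

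Pooled rejection rates, FAS against all observed, using |t| > 1.99 rather than Kenward-Roger:

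- First row: 7.4% v 6.4% when the true difference is 0, and 51% v 40% when it is −0.5.
- Equal split: 5.8% v 5.8%, and 38% v 39%.

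**6. Cross-checks**

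A simulation of selection alone, without the mixed model, gave Period 1 biases of −0.255 (4 leavers, 0.65), −0.192 (3, 0.65), −0.313 (4, 0.8) and −0.380 (4 worst, 0.8), which agree with the table.

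For the pooled bias, the retained subjects' Period 2 ratings are selected too, so roughly: pooled ≈ ½ × Period 1 bias × (1 − between/within correlation).

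- First row: ½ × −0.253 × (1 − 0.2/0.65) = −0.088 (simulated −0.084)
- 4 worst: ½ × −0.379 × (1 − 0.1/0.8) = −0.166 (simulated −0.160)

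**7. Precision**

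If four leavers, split evenly, each had a full Period 1 outcome, the Period 1 SE would fall from 1.25 × √(2/15) = 0.456 to 1.25 × √(2/17) = 0.429, a variance ratio of 15/17 = 0.88. Power for a difference of 1 would rise from 56% to 62%. In the simulation, where leavers lack Day 42, the variance gain was about 6%. Pooled precision did not change (SD 0.29 both ways).

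**The case against.** The rule is prespecified and consistent across both documents. The synopsis defines evaluability in the same way and inflates the sample for it, and the sizing uses a paired t-test. The primary objective is safety, analysed with partial completers kept. Efficacy testing is declared exploratory, and subjects excluded from the FAS are listed with reasons. The larger biases require every exclusion to fall on NB-001 in Period 1, and nothing in the documents supports that split. At three to one, the pooled bias of 0.037 is about 0.13 of the estimator's SD of 0.29, and the Period 1 bias of 0.125 is under a third of its standard error. The rejection rates of 7.4% and 6.4% under no effect are hardly distinguishable at 1500 trials. The near-zero bias after the change follows from making dropout depend on an observed rating; with dropout driven by an unseen one, half the bias remains. The simulation gave leavers no ET rating.

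Most of this stands as a limit on weight. Day 42/ET is incomplete for efficacy rather than void, and some leavers may have no Period 1 rating to recover. But consistency between documents does not make selection on retention an intent-to-treat analysis. A listing of exclusions shows them without correcting the estimate. The paired sizing supports a both-periods set for paired tests, not for models that do not need it.

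**Conclusion.** The point holds. The FAS discards valid efficacy ratings because of a post-randomization event, in analyses that could use them. The harm depends on how dropout splits by treatment, which the documents do not give: near zero if balanced, about 0.04 points pooled and 0.13 in Period 1 at three to one, and at the one-sided extreme 0.02 to 0.16 pooled and 0.19 to 0.38 in Period 1, or 19% to 38% of the planned 1-point effect. These figures rest on 3 or 4 exclusions, all before a Period 2 rating, on the assumed correlations, and on dropout explained by the Day 28 rating. If it depends on the unseen Day 42 rating, including the data only halves the bias. The exclusion reading itself needs no assumptions. With exploratory efficacy testing, this is a change that should be made rather than one the trial cannot proceed without.

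**What to change.** - **FAS (SAP 4.2, Protocol 15.1 and synopsis):** enrolled-set subjects who were randomized, took IP and have at least one valid post-baseline efficacy evaluation in either period, analysed as randomized. Call it modified intent-to-treat. Use it for the pooled and by-period mixed models and the Day 42/ET efficacy summaries.
- **Evaluable set:** a separate set rated in both periods, for the sample-size count, the Wilcoxon signed-rank and McNemar tests, and a sensitivity analysis. Amend the SAP sentence that calls FAS subjects evaluable.
- **O'Brien test (SAP 4.4.7.5):** state which set feeds it. Use the FAS if its t-statistics come from the mixed models, and the both-periods set if they come from paired differences.
- **ET ratings:** state how an off-schedule ET rating is assigned to a visit in the models.
- **SAP 4.7:** record the change. Protocol section 15 allows the SAP to modify methods, so the protocol wording could follow at the next amendment.

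Make the change before unblinding and database lock. It costs wording and one extra analysis set, with no new data or subjects. It removes bias only as far as observed ratings explain dropout, and it hardly changes pooled precision.
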